The initiation of the contraceptive implant at 4-8 weeks postpartum has been studied in breastfeeding women; no change in volume or composition of breast milk was found. [17] A study looking at growth of breastfed infants found that at three year follow up, child growth and development was no different between users of implant and copper intrauterine device (IUD). [18] Additionally, Brito et al. (2009) documented no diminished weight gain in infants of women who were exclusively breastfeeding and obtained a contraceptive implant at 6 weeks postpartum. [19] The literature demonstrates immediate contraceptive implant insertion does not alter volume of breast milk intake by newborns. Braga et al. (2015) evaluated breast milk volume when the ENG implant was inserted immediately postpartum and found no difference in the median breast milk intake by newborns between women who were randomized to have the implant inserted within 48 hours after delivery and those who obtained no method of contraception. The study also documented similar weights of newborns between both groups at six weeks following delivery, adding to safety data on effects of immediate insertion on breastfeeding. [20]

Objectives and hypotheses:

This is a non-inferiority randomized controlled trial:

Our objective is to determine whether time to lactogenesis stage II differs between immediate delivery room insertion (0-2 hours following delivery) and delayed postpartum insertion (24-48 hours following delivery) of the contraceptive implant in the postpartum ward prior to medical discharge. We hypothesize there will be no significant difference in time to lactogenesis stage II between the two groups.

Design & Methodology:

This is a non-inferiority randomized controlled trial.

Peripartum women with healthy, term newborns who plan to use the contraceptive implant (etonogestrel implant, Nexplanon) for postpartum contraception and intend to breastfeed will be randomized to receive:

- **Arm 1: Immediate delivery room insertion (0-2 hours following delivery)**
- **Arm 2: postpartum room insertion (24-48 hours following delivery)**

The primary outcome is time to lactogenesis stage II (defined as the initiation of copious milk secretion) as documented by maternal perception by a validated tool. [21]

Secondary outcomes include breastfeeding continuation and exclusivity, contraceptive continuation, patient satisfaction, pregnancy rates, timing and number of follow up postpartum care visits.

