Trained providers will use standard protocol to place the contraceptive implant either in delivery room or in postpartum ward after delivery. We will collect information on the timing of delivery and the time of implant insertion. A card indicating date of insertion and expiry date will be given together with post insertion instructions on wound care. Participants will be monitored daily by the research staff, in the first seven days postpartum, or until lactogenesis reported, beginning at 24-hours following delivery, to determine time to lactogenesis stage II using a validated tool. [21] Patients will be asked: "Has your milk come in yet?" and "When did your milk come in?" If the patient answers yes to first question the response will be recorded to the nearest hour. Participants will be asked: "How many times have you tried to breastfeed before your milk came in? Delayed lactation will be defined as no lactation by 72-hours following delivery. Lactation failure will be defined as no lactogenesis by 120-hours following delivery. Post-discharge follow-up questionnaires will involve telephone interviews, text messaging, electronic communication as needed, until lactogenesis occurs and at 4-8 weeks, 3, 6, and 12 months. Participants will be asked about length of exclusive breastfeeding, supplementation rates, side effects, continuation or change of contraceptive use (including abstinence or withdrawal), dates of postpartum medical visits, pregnancy, satisfaction with the contraceptive implant, resumption of vaginal intercourse, and infant weight. Once the participant completes the 12 month follow up questionnaires, they will have completed the study.

Criteria for selection of subjects:

Exclusion criteria:

Contraindication to implant insertion such as history of breast cancer. Hypersensitivity to any components of implant. Women who are not English or Spanish speakers or fluent in either language. Women who delivery infants that are not healthy.

Inclusion criteria:

- Pregnant women who are patients of the Stanford University Obstetrics service
- Pregnant women who delivery a healthy infant, regardless of gestational age.
- Intend to breastfeed
- Desire the contraceptive implant as their method of contraception
- Agree to be randomized to delivery room vs. postpartum ward insertion

Description of the drugs & devices to be studied:

Not applicable.

Follow up procedure:

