Participants will receive brief telephone follow-up, including an interview at 4-8 weeks, 3, 6, and 12 months from date of delivery.

Criteria for discontinuation:

Participants who experience complications during labor and delivery or whose infants have medical problems will be discontinued. Patients who change their mind about contraceptive implant use will be discontinued. Intention to treat analysis will be employed.

Lab and other investigations:

Not applicable.

Data Management

Data will be collected on REDCap software, will be coded, monitored, and verified.

Data Analysis

SPSS version 23 will be used for data analysis.

Number of subjects and statistical power:

Based on previous reports of women with uncomplicated vaginal deliveries, mean time to lactogenesis stage II is 54 hours with a standard deviation of 12 hours. [21] If there is truly no difference between immediate insertion and delayed insertion of the contraceptive implant on time to lactogenesis stage II, then 68 patients are required to be 80% sure that the lower limit of a one-sided 95% confidence interval (or equivalently a 90% two-sided confidence interval) will be above the non-inferiority limit of a mean difference of 12 hours (alpha 5%; SD 18). Sealedenvelope.com was used to calculate

sample size based on these parameters. A non-inferiority margin of 12 additional hours is chosen to be relevant because common medical interventions like epidural anesthesia, cesarean section, labor induction, have been to delay stage II lactogenesis by up to 12 hours. [22] To account for potential participant dropout, 82 participants will be recruited.

Study limitations:

This is not a blinded study; appropriate blinding would require the use of placebo implants and additional procedures. We do not anticipate our inability to blind participants and providers to impact our primary outcome of time to lactogenesis stage II.

Our recruitment will be limited to the Stanford Obstetrics and Gynecology service. Thus internal validity will not be a concern, but this clinic's population is not representative of the diversity of the female population in the United States or of women giving birth in the United States.

Based on this study's inclusion and exclusion criteria, results cannot be extrapolated to women with some medical conditions, complications, during labor and delivery, or who have infants with medical problems.

Duration of project:

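### Intention-to-treat is the only analysis named for a non-inferiority trial of insertion timing; a per-protocol analysis on the protocol's own windows should be pre-specified beside it

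*Combined protocol and SAP*

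**What the plan says.** Design & Methodology states "This is a non-inferiority randomized controlled trial" and defines the arms by time since delivery: 0-2 h in the delivery room (Arm 1) and 24-48 h on the postpartum ward (Arm 2).

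Under Study Procedures, women are randomised when admitted to labor and delivery. The same section says "We will collect information on the timing of delivery and the time of implant insertion", but no analysis is assigned to those times.

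On analysis, Criteria for discontinuation ends with "Intention to treat analysis will be employed". The Data Analysis section consists of "SPSS version 23 will be used for data analysis". No per-protocol set, sensitivity analysis or adherence table is named, and no rule covers an insertion at 2-24 h, after 48 h, or not done.

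The paragraph that names ITT also says "Patients who change their mind about contraceptive implant use will be discontinued", and applies the same to women with labor and delivery complications or infants with medical problems. Main problems anticipated lists complications and change of mind as expected difficulties.

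**The concern.** In a superiority trial, women who do not receive their assigned treatment usually make the result conservative. In a non-inferiority trial the effect can run the other way. If an Arm 1 woman gets her implant late or not at all, and her time to lactogenesis then resembles that of an Arm 2 woman, the observed difference moves toward zero. That is the direction of the claim the trial hopes to make. Early insertion in Arm 2 does the same.

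Allocation is fixed before the course of delivery is known, and the Arm 1 window is short, so some departures are plausible. At stake is whether a finding of non-inferiority could be read as showing that insertion at 0-2 h does not delay lactogenesis by 12 h or more, or only that assigning women to it does not.

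**Working it through.** **Inputs from Number of subjects and statistical power:** margin 12 h; SD 18 h; one-sided 5% (90% two-sided confidence interval); 80% power; true difference zero; 68 women needed, 82 recruited. Allocation is by blocks with no ratio given; 1:1 is assumed, so 34 or 41 per arm.

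**The plan's own figure.** n per arm = 2 × (1.645 + 0.842)² × 18² / 12² = 27.8, rounded up to 28, or 56 in total. The stated 68 does not reproduce from these inputs. That is a separate matter; 34 per arm is used below because it is the plan's number.

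**Dilution under ITT.** Suppose the true delay with assigned timing is exactly 12 h, so that non-inferiority should be claimed only 5% of the time. Let c be the share of Arm 1 whose outcome fully resembles Arm 2's, with all outcomes kept. No value of c is given in the documents, so it is an assumption.

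- Expected ITT difference = 12 × (1 − c).
- SE = 18 × √(2/34) = 4.366 h.
- False non-inferiority rate = Φ(12c/SE − 1.645).

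| c | ITT difference | 12c/SE | False non-inferiority rate |
|---|---|---|---|
| 0 | 12.0 h | 0 | 5.0% |
| 5% | 11.4 h | 0.137 | 6.6% |
| 10% | 10.8 h | 0.275 | 8.5% |
| 20% | 9.6 h | 0.550 | 13.7% |

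Simulation with a pooled t-interval (100,000 runs) gave 8.5% at c = 10% and 13.4% at c = 20%.

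The section also quotes an SD of 12 h from earlier reports. With that, SE = 12 × √(2/34) = 2.910 h and the rates are 10.9% (10%) and 20.6% (20%). The SD used for sizing is 18 h, so the table is the main illustration.

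**Which departures dilute.**

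- Arm 1 late or missed: dilutes, fully only if the woman's outcome becomes like Arm 2's. A slightly late insertion may keep much of any effect.
- Arm 2 early: dilutes. If 10% of each arm effectively received the other timing, the difference would be 12 × (1 − 0.10 − 0.10) = 9.6 h, as in the last row.
- Arm 2 late or missed: need not dilute. It could widen the difference if insertion at 24-48 h itself has an effect.

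**Power of a per-protocol analysis.** Power = Φ(12/(18 × √(2/n)) − 1.645). From 41 per arm with 20% excluded, n = 32.8, SE = 4.445 h, and power = Φ(2.700 − 1.645) = 85%. With 30% excluded, n = 28.7 and power is 81%. These figures precede any requirement that two analyses agree.

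**The case against.** **ITT is not wrong.** For the effect of assigning a woman to delivery-room insertion, it keeps its 5% error rate. The Project Summary gives a service aim, making earlier insertion possible, for which that is a legitimate question. This stands. A reader might infer that the trial's error rate is broken. The documents do not support that: the inflation concerns only the effect of timing actually received.

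**Off-window insertion is inferred.** No section mentions insertions at 2-24 h or after 48 h, and no rate is given. This also stands. The inference rests on randomisation at admission and the two-hour window.

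**The non-adherers the plan does name may not be in the analysis.** Women who change their mind are discontinued, and those with complications are described as no longer eligible. If their outcomes are not collected, they dilute nothing, and the problem becomes exclusion after randomisation, in conflict with ITT. The plan does not say which applies. Off-window insertions are unaffected by this objection, because no rule discontinues those women.

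**Poor adherence does not always pull the arms together.** A reader might infer that it does, but late or missed Arm 2 insertions need not. Pooling non-adherence across arms into one diluting share would overstate the effect.

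**Per-protocol analysis brings its own bias.** The sample-size section says cesarean section, epidural and induction can delay lactogenesis by up to 12 h. If such deliveries also disrupt the 0-2 h insertion (an assumption), excluding those women removes slow-onset cases mainly from Arm 1, which again favours non-inferiority. Requiring agreement cannot make a false claim more likely than ITT alone, but it is not complete protection.

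**Conclusion.** The concern holds as a missing supporting analysis and a cheap improvement. For a non-inferiority claim about insertion timing, ITT is the only analysis named, and the recorded times that would show adherence have no planned use.

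The direction of the bias is clear for late or missed Arm 1 insertions and early Arm 2 insertions, provided the outcomes are kept. Its size is not known from the documents. The illustrated rise from 5% to between 6.6% and 13.7% rests on 34 per arm, SD 18 h, a true delay at the margin, and an assumed 5% to 20% of Arm 1 losing the whole 12 h contrast. For a given rate of Arm 1 non-adherence these are upper-end figures.

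The documents do not support the stronger readings that ITT should be replaced, or that a false claim is likely.

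**What to change.** 1. Keep ITT. Pre-specify beside it a per-protocol analysis of women whose recorded delivery and insertion times fall in the protocol's own window for their arm (0-2 h or 24-48 h), with the same 90% two-sided interval and 12 h margin. Because the trial is open-label, fix the definition before outcomes are examined.
2. Support the non-inferiority claim only when the two analyses agree. With the difference taken as immediate minus delayed, the upper limit should be below 12 h in both.
3. Tabulate by arm the insertions at 2-24 h, after 48 h and not done. Report reasons for per-protocol exclusion by arm, and by mode of delivery where available, so that selection can be judged.
4. Reconcile the discontinuation rule with the ITT sentence in the same paragraph, stating whether the lactogenesis outcome of women who change their mind or have complications is still collected and analysed.

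**Cost.** Items 1 to 3 need a few sentences and one more run, mostly on times the plan already records. The per-protocol set is smaller: about 85% power at SD 18 h with 20% excluded from 41 per arm, and less once both analyses must agree. Room depends on the target: 82 − 56 = 26 women can be lost against the recomputed size, but only 82 − 68 = 14 against the stated one, dropout included. Following women whose implant is never placed goes beyond what the plan clearly collects. Selection bias in the per-protocol set remains possible and should be acknowledged in the report.

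### The stated 80% power at 68 women follows neither from the SD of 18 h used in the calculation nor from the 12 h cited beside it, and the 18 h has no source.

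*Combined protocol and SAP*

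**What the plan says.** All the relevant text is one paragraph of the protocol, under the heading Number of subjects and statistical power.

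- Evidence cited for the endpoint, limited to uncomplicated vaginal births and attributed to reference 21: "mean time to lactogenesis stage II is 54 hours with a standard deviation of 12 hours".
- Planning assumption: "If there is truly no difference between immediate insertion and delayed insertion of the contraceptive implant on time to lactogenesis stage II".
- Result: "68 patients are required to be 80% sure".
- Criterion: "the lower limit of a one-sided 95% confidence interval (or equivalently a 90% two-sided confidence interval".
- Margin and SD entered: "the non-inferiority limit of a mean difference of 12 hours (alpha 5%; SD 18". The margin is repeated a few lines later: "A non-inferiority margin of 12 additional hours is chosen to be relevant".

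An online calculator is named as the tool. Recruitment is set at 82 to allow for dropout, with no rate given. No other section mentions 18 h or explains it.

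**The concern.** The paragraph holds two SDs for one endpoint in one unit, and the variance used is (18/12)² = 2.25 times the variance cited. That prompts a check of which SD the 80% belongs to. It belongs to neither.

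The SD and the power together tell the reader how precise the comparison should be and how many women can be lost before the trial is too small. The second question is a practical one here. The section on main problems anticipated expects slow recruitment, and it expects some women to lose eligibility after enrolment. If 68 is taken as the minimum for 80% power, a shortfall of a few women looks more serious than the plan's own inputs imply.

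**Working it through.** **Inputs from the plan:** margin M = 12 h; one-sided alpha 5% (z = 1.645); power 80% (z = 0.842); true difference 0; SD 18 h as entered, 12 h as cited. **Assumed, because not stated:** 1:1 allocation, so 34 per arm at 68, and a comparison of two means. With a true difference of zero, the calculation is the same whichever end of the interval is set against the limit.

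**Step 1. Try to reproduce 68.** Number per arm: n = 2 × (1.645 + 0.842)² × SD² / M².

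- SD 18: 2 × 6.185 × 324 / 144 = 27.8, so 28 per arm and 56 in total. The noncentral t calculation gives 29 per arm, 58 in total.
- SD 12: 2 × 6.185 × 144 / 144 = 12.4, so 13 per arm and 26 in total (28 by t).

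Neither gives 68.

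**Step 2. Try nearby settings at SD 18 (normal approximation).** One-sided 2.5% gives 72. Power of 85% gives 66, and 90% gives 78. An 11 h margin does give 68, but the plan states 12 h twice. One further route arrives at both totals: 28 × 1.2 = 33.6, so 34 per arm or 68, and then 68 × 1.2 = 81.6, so 82. That would mean a 20% allowance was applied twice. This is a guess from the numbers; the plan does not say it.

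**Step 3. Power at 68.** Normal approximation: power = Φ(M / (SD × √(2/34)) − 1.645). For SD 18, the standard error is 18 × 0.2425 = 4.37 h, 12 / 4.37 = 2.75, and Φ(1.10) = 0.865. For SD 12, the standard error is 2.91 h, 12 / 2.91 = 4.12, and Φ(2.48) = 0.993. The t column uses the noncentral t with 66 degrees of freedom.

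| SD (h) | Power at 68, normal | Power at 68, t |
|---|---|---|
| 12 (cited) | 99.3% | 99.3% |
| 18 (entered) | 86.5% | 85.9% |
| 20 | 79.7% | 78.9% |
| 24 | 66.2% | 65.4% |

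**Step 4. Which SD makes the statement true?** Solving for SD at 34 per arm: 12 × √(34/2) / 2.487 = 19.9 h. That figure is not in the plan.

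**Step 5. Expected precision at 68.** Half-width of the two-sided 90% interval = t(0.95, 66) × SD × √(2/34): 4.9 h for SD 12 and 7.3 h for SD 18.

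**The case against.** The best defence is that two SDs in one paragraph need not conflict. The 12 h is limited, in its own sentence, to uncomplicated vaginal deliveries. The eligibility list does not restrict mode of delivery, and the plan says cesarean section, epidural and induction can delay onset by up to 12 h. A mixed population should be more variable, and planning on a larger SD is cautious. The SD entered is also printed beside the power, so nothing is hidden.

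Most of this stands. A reader might infer that 18 h is a mistake, that 12 h should replace it, or that the gap between the two is what makes the 80% wrong. The documents support none of these. The 12 h comes from a narrower group. Replacing 18 h with it would remove the plan's only cushion for extra variability. The 80% would also still be wrong if 18 h were the only SD in the paragraph. Nor is the trial shown to be underpowered, since power at 68 exceeds 80% under both SDs.

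Two things survive the defence. First, it does not rescue the arithmetic: 68 at 80% fails on the plan's own SD of 18 h. Second, the plan's figures do not by themselves lead to 18 h. As an illustration, suppose a within-group SD of 12 h and half the women delayed by the full 12 h. The overall SD is then √(144 + 0.25 × 144) = 13.4 h. The criteria for discontinuation also remove women with complications during labor and delivery, which narrows the population again. So 18 h may be reasonable, but the reason has to come from the sponsor.

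**Conclusion.** Wrong as written, and minor. On the plan's inputs, 80% power needs 56 to 58 evaluable women rather than 68, an excess of 10 to 12. Power at 68 is about 86% at SD 18 and about 99% at the cited SD 12.

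The direction is conservative, and the margin, the confidence level and the decision rule are unaffected. The absence of a reason for 18 h is a gap in documentation, not a demonstrated error. It still matters somewhat, because nothing shows that 18 h is an upper bound, and power at 68 falls to about 79% at 20 h and about 65% at 24 h.

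The figures rest on 1:1 allocation, a comparison of means and a true difference of zero. Only the last is stated in the plan.

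**What to change.** In the section on number of subjects and statistical power:

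1. Keep 18 h as the single planning SD. Present the 12 h as background for uncomplicated vaginal deliveries.
2. Either restate power at 68 evaluable women as about 86%, or restate the number needed for 80% as 56 to 58.
3. Give the sponsor's actual source or reason for 18 h. A rationale should not be supplied after the fact if none was used.
4. Add power at 68 over a range of SDs: about 99% at 12 h, 86% at 18 h, 79% at 20 h and 65% at 24 h.
5. State the allocation ratio and the comparison on which the calculation rests.

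The cost is a few sentences of protocol text. Enrolment of 82, the study procedures and data collection do not change.

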Patients will be counseled about risks and benefits of contraceptive options and will be counseled appropriately regarding risks and benefits of subdermal contraception implant, as well as the unknown effects of early progestin administration on breastfeeding. Patients will not be eligible for the study unless they have been consented for a postpartum contraceptive implant prior active labor. If the patients meet inclusion criteria they will be invited to participate in the study and consent will be obtained. When a study patient is admitted to L&D, they will be met by research personnel and be randomized to one of the two arms. Participants will be randomized through block randomization—allocation will be sealed in an opaque envelope. The patient, provider, and research staff will be aware of arm allocation, this is not a blinded study. At this time, baseline data will be collected on patient age, gravidity, parity, breastfeeding experience on REDCap with a designated Ipad.

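### The stated 68 patients for 80% power does not follow from the printed inputs, which need 56 (58 by t); 68 gives about 86%

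*Combined protocol and SAP*

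**What the plan says.** The whole calculation stands in one paragraph of the combined protocol and SAP, under Number of subjects and statistical power.

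- True difference: "If there is truly no difference between immediate insertion and delayed insertion", that is, zero.
- Power, confidence level and size: "then 68 patients are required to be 80% sure that the lower limit of a one-sided 95% confidence interval", which the text equates with a two-sided 90% interval.
- Margin, alpha and SD: "will be above the non-inferiority limit of a mean difference of 12 hours (alpha 5%; SD 18" hours). The margin is repeated in the justification: "A non-inferiority margin of 12 additional hours is chosen to be relevant".
- Source: an online calculator is said to have given the "sample size based on these parameters".
- Dropout, added afterwards: "To account for potential participant dropout, 82 participants will be recruited". No dropout rate is given.

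The same paragraph cites a mean of 54 hours and an SD of 12 hours from previous reports. It then calculates with 18 and does not explain the change.

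Two related details are left open. Study Procedures says "Participants will be randomized through block randomization" but gives no ratio. Data Analysis says only that "SPSS version 23 will be used for data analysis", so the test for the primary comparison is not named.

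**The concern.** A sample size statement should be reproducible from its own inputs. Here every input is printed except the allocation ratio, the text says the size came from those inputs, and yet the standard formula gives a clearly smaller number. The gap of 10 to 12 patients, or about 6 percentage points of power, is too large for rounding or for the choice between normal and t methods.

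What is at stake is knowing what power was planned, and so how much loss the trial can absorb. The plan discontinues women with labor or delivery complications, women whose infants have medical problems, and women who change their mind about the implant. It also expects slow recruitment. Whether 58 evaluable women would still be enough depends on which printed figure is the wrong one.

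**Working it through.** **Inputs.** From Number of subjects and statistical power: margin M = 12 h, SD = 18 h, true difference 0, one-sided alpha 5% (z = 1.645), power 80% (z = 0.842). Assumed: 1:1 allocation, complete and roughly normal times compared as means, and a decision rule that excludes a delay of 12 h or more. The 68 is read as a total because 82 is the total to be recruited.

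**1. Size required by the printed inputs.**
n per arm = 2 × SD² × (z₀.₉₅ + z₀.₈₀)² / M²
(1.645 + 0.842)² = 6.1826
n = 2 × 324 × 6.1826 / 144 = 27.82, so 28 per arm = **56**.
By noncentral t, 28 per arm gives 79.3% and 29 gives 80.6%, so **58**.
The plan's 68 is not reproduced: it is 12 (21%) above 56 and 10 (17%) above 58.

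**2. Power that 68 gives on the printed inputs.**
SE = 18 × √(2/34) = 4.366
Power = Φ(12/4.366 − 1.645) = Φ(1.104) = **86.5%**; by noncentral t, **85.9%**.

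**3. Single changes or steps that reach 68.**

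| Change | Result |
|---|---|
| Power 85% instead of 80% | 32.35 → 33 per arm = 66 by z; by t, 33 per arm gives 84.95%, so 34 per arm = 68 |
| Dropout allowance already inside 68 | 56 × 1.2 = 67.2 → 68 in equal arms; the same factor again, 68 × 1.2 = 81.6 → 82 |
| Margin 11 h, or true difference 1 h | 2 × 324 × 6.1826 / 121 = 33.11 → 34 per arm = 68; power 80.9% (z), 80.2% (t) |
| Larger SD | about 19.6 to 19.9 h by z, about 19.4 to 19.7 h by t |

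The text states none of these for the 68.

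**4. Changes that do not reach 68.**
- One-sided alpha 2.5%: 35.32 → 36 per arm = 72 (74 by t).
- Power 90%: 38.54 → 39 per arm = 78 (80 by t).
- Allocation 1.5:1, 2:1 or 3:1: 59, 63 or 75 by z.
- The cited SD of 12 h: 2 × 144 × 6.1826 / 144 = 12.37 → 13 per arm = 26 (28 by t). At 34 per arm, SE = 12 × √(2/34) = 2.910 and power = Φ(12/2.910 − 1.645) = Φ(2.478), about 99%.

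**5. Why the origin matters.** Power by t:

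| Evaluable | Inputs as printed | 11 h margin or 1 h difference |
|---|---|---|
| 58 | 80.6% | 74.3% |
| 68 | 85.9% | 80.2% |
| 82 | 91.1% | 86.4% |

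**The case against.** The strongest reply is that the discrepancy is harmless. On the printed inputs 68 exceeds what 80% power needs, and 82 evaluable would give about 91%. No analysis, conclusion or participant risk changes. That stands, and it keeps the point minor.

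A second reply is that simple explanations exist. Power of 85% by the t method gives exactly 68 with every other printed input unchanged. A 20% allowance on 56 also gives 68, and the same factor takes 68 to 82. Both fit the arithmetic. Neither rescues the sentence: under the first the printed 80% is wrong, and under the second 68 is not the number required.

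A reader might go further in any of three directions, and the documents support none of them.

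- **That the trial is underpowered.** The printed inputs show the opposite.
- **That a misreported input would leave no surplus at 68.** That holds for an 11 h margin, a 1 h true difference or a larger SD, but not in general. If the cited SD of 12 h were the real one, 68 would give about 99% power.
- **That dropout was counted twice, or that 80% is a misprint for 85%.** Both are possible origins only. The plan gives no dropout rate and no record of the calculator entries.

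**Conclusion.** The point holds as a minor reporting error. The printed inputs need 56 evaluable participants (58 by t) for 80% power, and 68 gives 86.5% (85.9% by t). At least one of the 68, the 80% and the printed inputs is therefore wrong, and the documents do not identify which. If the inputs are as printed, the error is on the safe side.

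The figures rest on the assumptions listed with the inputs. The allocation ratio is the only assumed input to the formula, and none of the ordinary unequal ratios tried gives 68. The unexplained move from the cited SD of 12 h to 18 h belongs to the same check, but it does not explain the 68.

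**What to change.** Look up the values entered in the calculator, and establish whether 68 already includes a dropout allowance.

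- **If the inputs are as printed,** restate along these lines: *56 evaluable participants (58 by t) give 80% power; 68 evaluable (34 per arm, 1:1) give about 86% for a 12 h margin, SD 18, one-sided alpha 5% and no true difference.*
- **If an input or the target power differed,** correct it in the text and restate the size and power to match.
- **In either case,** state the allocation ratio, say why 18 h was used when 12 h is cited, and give the dropout rate behind 82. Confirm the basis of that target, and state how many losses can be tolerated, only once the inputs are known.

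The cost is one look-up and one rewritten paragraph. No added patients are needed.
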